4.3 Inclusion Criteria

Individuals who meet all of the following criteria are eligible for enrollment as study participants:

1. Must be able to understand and provide informed consent.
2. Male or Female, 18-70 years of age at the time of enrollment (all races and ethnicities).
3. Negative crossmatch (virtual or physical) at time of transplant.
4. First dose of Study Drug must be given no less than 8 weeks, no more than 20 weeks post-transplant.
5. First time renal transplant who has been treated with belatacept from the time of transplant, receiving tacrolimus (target trough 3-5 ng/ml), mycophenylate mofetil (or mycophenolic acid or azathioprine), prednisone (also see exclusion criteria).
6. eGFR ≥ 40 ml/min/m² (using 2021 CKD-EPI equation).
7. Must have prior documented evidence of EBV seropositivity.
8. Female study participants of childbearing potential must have a negative pregnancy test on Day 0 prior to receiving the first dose of study drug.
9. Agreement to use contraception; according to the FDA Office of Women's Health (<http://www.fda.gov/birthcontrol>), there are a number of birth control methods that are more than 80% effective. Female study participants of child-bearing potential and men must consult with their physician and determine the most suitable method(s) from this list to be used from the time that study treatment begins until after study completion.
10. Vaccines up to date as per DAIT guidance for patients in transplant trials. (Refer to Appendix 2: DAIT Vaccine Guidance for Patients in Interventional Adult Transplant Trials)

11. Study participants must have a negative purified protein derivative (PPD) or negative testing for tuberculosis using an approved IGRA blood test, such as QuantiFERON®-Gold TB or T-SPOT-TB assay. PPD or IGRA testing must be documented to have been performed within the 52 weeks before enrollment. Patients with latent TB may become eligible according to local or national guidelines following completion of treatment.

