4.4 Exclusion Criteria

Individuals who meet any of these criteria are not eligible for enrollment as study participants:

1. Inability or unwillingness of a study participant to give written informed consent or comply with study protocol.
2. Recipient of previous organ transplant of any type.
3. Multi-organ transplant.
4. cPRA >80 at time of enrollment.
5. History of any episode of biopsy-proven Banff rejection (including borderline rejection or any grade of acute TCMR) prior to enrollment.
6. History of any malignancy including lymphoma within 5 years of enrollment. Study participants with curatively treated non-melanomatous skin cancer or curatively treated cervical carcinoma in situ may be enrolled.
7. Any past or current issue which in the opinion of the investigator may pose additional risks to the participant in the study, may interfere with the study participant's ability to comply with the study requirements or that may impact the quality or interpretation of the data obtained from the study.
8. Human immunodeficiency virus (HIV): individuals known to be HIV positive.
9. Hepatitis C virus: any study participant who receives a kidney from a seropositive or HCV RNA PCR positive donor is ineligible. Any study participant who was HCV RNA PCR positive at transplant is ineligible. Any study participant with a history of HCV seropositivity or HCV infection who has not met criteria for sustained spontaneous clearance or sustained viral response to therapy is ineligible.
10. Hepatitis B virus: Individuals with any of the following are NOT eligible:
 - Recipient or donor positive for hepatitis B surface antigen (HBsAg)
 - Recipient or donor positive for antibodies to hepatitis B core antigen (anti-HBc)
 - Recipient or donor known to have had a positive HBV DNA PCR
11. Evidence of CMV viremia or clinical CMV infection at any time after transplant.
12. Kidney recipients who were CMV seronegative who received an organ from a CMV seropositive donor.
13. BK viremia of greater than 4.3 DNA log copies/ml (greater than 20,000 copies/ml) at any time post-transplant.
14. Active uncontrolled infection within 1 month of enrollment.
15. Clinically significant proteinuria (urinary protein/Cr ratio >1.0).
16. Receiving belatacept at a dose other than 5 mg/kg body weight.
17. Receiving mycophenolate mofetil at a dose of less than 1000 mg po QD (or mycophenolic acid or azathioprine equivalent).
18. Receiving prednisone at a dose greater than 5 mg po qd.

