14.2.2 Primary Analysis of Primary Endpoint(s)

Primary feasibility endpoint

The proportion of subjects who tolerate subcutaneous injections and are compliant with self-administration as measured by abatacept administration logs, autoinjector accountability, pharmacokinetics and pharmacodynamic measures of target molecule (CD86) receptor occupancy.

Primary Effectiveness (alloimmunity) endpoint

This primary effectiveness endpoint is the proportion of participants who remain free of biopsy proven acute T-cell mediated rejection (aTCMR) or antibody-mediated rejection (ABMR) as defined by Banff criteria at or before 12 months after transplantation.

Primary Safety Endpoints

- The cumulative incidence of serious adverse events
- Incidence of serious infection of special interest (e.g. requiring hospitalization or prolonged therapy, including but not limited to treatment ≥ 20 days)
- Incidence of patients with CMV viremia stratified by magnitude (≥ 35 but $< 10,000$ or $\geq 10,000$)

- Incidence of patients with BK viremia stratified by magnitude (undetected, >0 but < 1,000, ≥ 1,000 but <10,000 or ≥ 10,000 – 100,000, ≥100,000 or stratified by log, which is reported as a result)
- Incidence of any malignancy including PTLN

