14.4 Analysis Plan

Binary primary and secondary endpoints that occur at or before 12 months post-transplant will be summarized as a simple fraction and percentage and as a proportion. Confidence intervals (95%) for a one-sample proportion will be calculated for incidence rates using the Wilson score procedure with a correction for continuity.

Primary Effectiveness Endpoint: The cumulative incidence of alloimmunity (or alloimmunity-free survival) during the 12 months after transplantation will be estimated with the Kaplan-Meier method. The standard error of the Kaplan-Meier estimate will be calculated based on Greenwood's formula and used to construct 95% confidence intervals for the time-to-event curve. Patients with follow-up less than 1-year will be censored at last follow-up.

The cumulative incidence of primary safety endpoints during the 12 months after transplantation will be estimated with the Kaplan-Meier method.

A repeated-measures analysis of eGFR will be performed with a means model via the SAS MIXED Procedure (version 9.4; SAS Institute, Cary, NC), providing separate estimates of the mean eGFRs by time on study (between abatacept initiation and 12 months on treatment). The model will include one predictor (time on study as a categorical clinical visit variable). A compound-symmetric variance-covariance form in repeated measurements will be assumed for eGFR and robust estimates of the standard errors of parameters will be used to perform statistical tests and construct 95% confidence intervals (**Reference: Diggle et al**). The model-based means are unbiased with unbalanced and missing data, as long as the missing data are non-informative (missing at random). We will report the estimated mean eGFR and its 95% confidence at each month of follow-up and the time-averaged mean. A baseline-adjusted analysis will also be performed. Serum creatinine, total cholesterol, LDL, HDL, triglyceride and blood pressure plus the exploratory immunologic/mechanistic endpoints (peripheral blood T and B cell subsets) will be analyzed using the same plan described for eGFR.

This phase I trial will provide important estimates of variability (within-subject and between-subject standard deviation) for eGFR. The estimates of variability will be valuable to power future clinical trials since these variability estimates are essential components for sample size calculations.

15. Identification and Access to Source Data

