APPENDIX 1: SCHEDULE OF EVENTS

		Enrollment period is from Week 8 post transplant to week 20 post transplant ¹											
Visit (Months)	Screen	Post Transplant Mth 2	Post Transplant Mth 3	Post Transplant Mth 4	Post Transplant Mth 5	Post Transplant Mth 6	Post Transplant Mth 7	Post Transplant Mth 8	Post Transplant Mth 9	Post Transplant Mth 10	Post Transplant Mth 11	Post Transplant Mth 12	FC
Visit (Weeks)		8-11	12	16-19	20-23	24	28	32	36	40	44	52	
Visit Windows		+/- 5 days	+/- 5 days	+/- 5 days	+/- 5 days	+/- 5 days	+/- 5 days	+/- 5 days	+/- 5 days	+/- 5 days	+/- 5 day	+/- 5 day	
Informed Consent	X												
Inclusion/Exclusion Criteria	X												
Pregnancy Testing of WOCB (serum or urine)	X												
Questionnaires			X			X						X	
PRA-HLA Ab Screen	X					X						X	X
SAB I/II (DSA)	X		X (mo 3)			X						X	X
Hemoglobin A1c	X											X	
Hematology (CBC including differentials w/platelets)	X		X			X			X			X	X
Chemistry Panel	X		X			X			X			X	X
Viral Monitoring (BK and CMV)			X			X			X			X	X
Pharmacokinetics (PK) monitoring			X ²						X			X	X
Assessment of Adverse Events			→			→	→	→	→	→	→	→	X
Concomitant Medications Reviews			X			X	X	X	X	X	X	X	
Abatacept weekly administration			X			→	→	→	→	→	→	→	

		Enrollment period is from Week 8 post transplant to week 20 post transplant ¹											
Visit (Months)	Screen	Post Transplan t Mth 2	Post Transplan t Mth 3	Post Transplan t Mth 4	Post Transpla nt Mth 5	Post Transpla nt Mth 6	Post Transpla nt Mth 7	Post Transpla nt Mth 8	Post Transpla nt Mth 9	Post Transpla nt Mth 10	Post Transpl ant Mth 11	Post Transpl ant Mth 12	FC
Visit (Weeks)		8-11	12	16-19	20-23	24	28	32	36	40	44	52	
Visit Windows		+/- 5 days	+/- 5 days	+/- 5 days	+/- 5 days	+/- 5 days	+/- 5 days	+/- 5 days	+/- 5 days	+/- 5 days	+/- 5 day	+/- 5 day	
MMF ≥ 500mg p.o. BID	(X) ⁴	→				→	→	→	→	→	→	→	
Prednisone 5mg p.o. daily	(X) ⁴	→				→	→	→	→	→	→	→	
Tacrolimus (target trough 3-5ng/mL)	(X) ⁴	→				→	→	→	→	→	→	→	
Immunophenotyping		X				X			X			X	X
HLA DR/DQ Eplet Score		X											
Gene Expression		X				X			X			X	X

¹ Subjects will be enrolled no less than 8 weeks post transplant, no more than 20 weeks post-transplant. For subjects enrolled after Month 2, any study visit which occurred prior to subject enrollment does not apply.

² Initial PK test only required at first dose of Abatacept.

³ Collected when enrolled.

⁴ Doses required at enrollment.

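### The BK viremia safety endpoint has no baseline and is counted from transplantation, so viremia already present before abatacept, which entry allows up to 20,000 copies/ml, is reported as incident

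*Combined protocol and SAP*

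**What the plan says.** **Entry.** Exclusion 13 in section 4.4, repeated in the synopsis, removes patients with "BK viremia of greater than 4.3 DNA log copies/ml (greater than 20,000 copies/ml) at any time post-transplant". Any lower level is eligible. CMV is handled differently: exclusion 11 removes patients with "Evidence of CMV viremia or clinical CMV infection at any time after transplant".

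**Endpoint.** The synopsis and sections 3.2 and 14.2.2 list "Incidence of patients with BK viremia stratified by magnitude", with the strata "undetected, >0 but < 1,000, ≥ 1,000 but <10,000 or ≥ 10,000 – 100,000, ≥100,000" or, as an alternative, strata by log. None of the three places refers to a value before abatacept.

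**Time window.** Section 14.4 states: "The cumulative incidence of primary safety endpoints during the 12 months after transplantation will be estimated with the Kaplan-Meier method". It also summarises binary endpoints over the same post-transplant year as simple proportions, with continuity-corrected Wilson intervals. Section 4.3 states: "First dose of Study Drug must be given no less than 8 weeks, no more than 20 weeks post-transplant".

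**Population.** Section 14.2.1 takes everyone who starts abatacept into the modified intent-to-treat sample, whatever their BK status. There is one arm and the target is 18 patients.

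**The concern.** An incidence needs a population free of the event at the start and a clock that starts with the exposure of interest. This endpoint has neither. A patient who enters at 15,000 copies/ml and stays there is already in the 10,000 to 100,000 stratum and is counted as a case. So is a patient who had low-level viremia on belatacept and cleared it before the first abatacept dose, because the stated window covers that period.

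With no concurrent control, each patient's own pre-dose value is the only internal reference. The plan uses such a reference elsewhere: eGFR change is taken from abatacept initiation with a baseline-adjusted analysis, and donor-specific antibody is excluded at entry and then counted only if de novo. For CMV, the entry rule removes most of the problem. BK has no such protection. The result is a primary safety figure, in a trial meant to inform Phase II or III design, that mixes two treatment periods.

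**Working it through.** **1. Inputs.** From the documents: n = 18; entry limit 20,000 copies/ml; first dose at weeks 8 to 20; window of 52 weeks from transplantation; strata starting above 0. The strata carry no unit, and copies/ml is assumed. The documents do not give the share of patients viremic at entry (q) or the risk of new viremia on abatacept (r), so both are varied below.

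**2. The plan's own figures.** The entry limit agrees with itself: log10(20,000) = 4.30. The plan gives no figure for BK. The nearest is the table in section 13.9 for n = 18, where P(at least one event) = 1 − (1 − p)^18. At p = 0.05 this is 1 − 0.397 = 0.603 (plan 0.60), and at p = 0.10 it is 1 − 0.150 = 0.850 (plan 0.85). Both reproduce.

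**3. Overlap of entry range and strata.** The permitted range, above 0 up to 20,000, covers the two lowest positive strata and part of the 10,000 to 100,000 stratum.

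**4. Share of the window before abatacept.** 8/52 = 15% to 20/52 = 38%.

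**5. Direction.** Let k patients be viremic at entry and x develop new viremia. The plan reports (k + x)/n. New-onset incidence among those at risk is x/(n − k). The first is at least as large as the second whenever k + x ≤ n, which always holds. The any-viremia proportion can only move upward.

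**6. Size, over assumed values.** Counted proportion = q + (1 − q)r. Each patient viremic at entry adds 1/18 = 5.6 points.

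| Assumed q | P(at least one of 18 viremic at entry) | Counted if r = 0 | Counted if r = 10% | Pre-existing share of cases if r = 10% |
|---|---|---|---|---|
| 5% | 60% | 5% | 14.5% | 34% |
| 10% | 85% | 10% | 19% | 53% |
| 20% | 98% | 20% | 28% | 71% |

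**7. Illustrations, with the plan's continuity-corrected Wilson 95% interval.**
- Three patients enter viremic, none worsens and there are no new cases. The plan reports 3/18 = 16.7% (4.4% to 42.3%). Emergent incidence is 0/18 (0% to 21.9%).
- Two enter viremic and two are new. The plan reports 4/18 = 22.2% (7.4% to 48.1%). New onset among those negative at first dose is 2/16 = 12.5% (2.2% to 39.6%).

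**8. Worsening.** A patient who rises from 500 to 50,000 and one who stays at 15,000 both fall in the 10,000 to 100,000 stratum. A table by level cannot tell them apart.

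**The case against.** **The endpoint is descriptive.** The trial is an exploratory phase I study. The BK endpoint has no test, threshold, comparator or attribution rule, and its strata include an undetected category, so it may be meant as a distribution of patients by viral level. This stands in part: the plan does not attribute these cases to abatacept, and a reader who infers that it does goes beyond the text. But the endpoint is labelled an incidence and given a Kaplan-Meier cumulative incidence, and that reading needs a baseline.

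**Pre-dose PCR results must exist.** Exclusions 11 and 13 cannot be applied without post-transplant PCR results, and section 9.3 provides for quantitative PCR under the center's standard of care. This stands. The gap is that no result is designated as baseline or used in the endpoint.

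**Appendix 1 has no screening PCR.** A reader might infer this from the blank Screen cell in the viral monitoring row, and from the footnote "For subjects enrolled after Month 2, any study visit which occurred prior to subject enrollment does not apply", which on a literal Month 3 reading leaves later enrollees with a first scheduled PCR at Month 6. The table does not support that conclusion. The column with the first viral mark also holds the first questionnaire (given at enrollment), the first-dose pharmacokinetic sample and the start of abatacept, and the antibody row needs its own month 3 label there. The column may span the whole enrollment period. What can be said is that nothing places that sample before the first dose.

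**Treatment emergence is defined elsewhere.** Section 13.3.1 defines it for abnormal results as a rise in grade from baseline, and section 13.4.1 starts adverse event collection at first treatment. Some worsening would therefore be seen as adverse events. Neither rule is applied to this endpoint.

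**Only on-drug results will be counted.** Even so, a patient who enters viremic and stays viremic is positive at the first on-drug PCR and is counted.

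**Conclusion.** The point holds as a defect in the counting rule and time origin of one primary safety endpoint. As written, viremia present before conversion counts as incident, so the any-viremia proportion can only be inflated as a measure of incidence during abatacept. Tabulating by level does not separate stable from worsening viremia.

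The size cannot be computed from the documents, because entry prevalence is not given. It is 5.6 points per patient viremic at entry, and at an assumed prevalence of 5% or more the chance of at least one such patient is 60% or higher. The conclusion assumes that section 14 is applied literally. Section 14.2 defers detail to a statistical analysis plan, but section 14 itself contains no baseline rule.

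It does not follow that no baseline PCR is scheduled, that the plan blames abatacept for these cases, or that the entry threshold is wrong. The BK and CMV endpoints share one counting rule; only their entry populations differ.

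**What to change.** In section 14:
- Designate the last BK PCR on or before the first abatacept dose as baseline, and do the same for CMV, using results already needed for exclusions 11 and 13.
- Start the clock for this endpoint at the first dose.
- Report new-onset viremia among baseline-negative patients and, separately, a rise to a higher stratum among baseline-positive patients.
- Add a shift table of baseline stratum against maximum post-dose stratum.
- Make the top BK strata exclusive: 10,000 to <100,000, and ≥100,000. At present a value of exactly 100,000 fits both.

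In Appendix 1, state that the enrollment-period viral sample is taken before the first dose.

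The cost is one baseline field on the case report form and one small table. No new test is needed where a standard-of-care result exists. The baseline-negative denominator may fall slightly below 18, which widens the interval: in the example with three patients viremic at entry, new onset would be 0/15, with an upper limit of (z² + 1 + z√(z² + 2 − 1/15)) / (2(15 + z²)) = (4.841 + 4.710)/37.683 = 25.3%, against 21.9% for 0/18. No change to the eligibility threshold is proposed.

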14.2.3 Analyses of Secondary and Other Endpoint(s)

Additional Effectiveness Endpoints

- Proportion of subjects experiencing the composite outcome of death or allograft failure at or before 12 months after transplantation.
- Proportion of subjects with biopsy proven acute T-cell mediated cellular rejection (BP-aTCMR) within 12 months of transplantation.
- Proportion of subjects treated for rejection with any of the following: i) corticosteroids within 12 months, ii) T-cell depleting therapy within 12 months, iii) any other treatment for rejection within 12 months of transplantation.
- Proportion of subjects treated for acute rejection due to clinical suspicion rather than BP-aTCMR or BP-aABMR) within 12 months of transplantation.
- Proportion of subjects with biopsy proven active antibody mediated rejection (BP-aABMR) within 12 months of transplantation.
- Proportion of subjects and time to event for the changes in allograft biopsies for the 5 categories of aTCMR specified in the Banff schema.
- Proportion of subjects who develop de-novo donor specific antibody by 12 months
- Change in eGFR between abatacept initiation and 12 months on treatment.
- Days to events (TCMR, ABMR, de-novo DSA formation, graft loss)

14.2.4 Analyses of Exploratory Endpoint(s)

Clinical

Patient preferences and attitudes toward subcutaneous and intravenous route of administration will be assessed based on questionnaires administered at enrollment and at study visits at month 6 and 12 months post-initiation of abatacept.

Immunologic/Mechanistic

- CD86 receptor occupancy on PBMC will be assessed before the initial dose of Abatacept, and prior to abatacept administration at months 9, and 12 months post-transplantation.
- The incidence and breadth of anti-HLA antibody (including DSA) development over time (evaluated at screening, 3, 6 and 12 post-transplant).
- Peripheral blood T and B cell subsets will assessed at 6, 9, and 12 months post-transplant.

14.3 Interim Analyses

There is no planned interim analysis for this study.

14.4 Analysis Plan

Binary primary and secondary endpoints that occur at or before 12 months post-transplant will be summarized as a simple fraction and percentage and as a proportion. Confidence intervals (95%) for a one-sample proportion will be calculated for incidence rates using the Wilson score procedure with a correction for continuity.

Primary Effectiveness Endpoint: The cumulative incidence of alloimmunity (or alloimmunity-free survival) during the 12 months after transplantation will be estimated with the Kaplan-Meier method. The standard error of the Kaplan-Meier estimate will be calculated based on Greenwood's formula and used to construct 95% confidence intervals for the time-to-event curve. Patients with follow-up less than 1-year will be censored at last follow-up.

The cumulative incidence of primary safety endpoints during the 12 months after transplantation will be estimated with the Kaplan-Meier method.

A repeated-measures analysis of eGFR will be performed with a means model via the SAS MIXED Procedure (version 9.4; SAS Institute, Cary, NC), providing separate estimates of the mean eGFRs by time on study (between abatacept initiation and 12 months on treatment). The model will include one predictor (time on study as a categorical clinical visit variable). A compound-symmetric variance-covariance form in repeated measurements will be assumed for eGFR and robust estimates of the standard errors of parameters will be used to perform statistical tests and construct 95% confidence intervals (**Reference: Diggle et al**). The model-based means are unbiased with unbalanced and missing data, as long as the missing data are non-informative (missing at random). We will report the estimated mean eGFR and its 95% confidence at each month of follow-up and the time-averaged mean. A baseline-adjusted analysis will also be performed. Serum creatinine, total cholesterol, LDL, HDL, triglyceride and blood pressure plus the exploratory immunologic/mechanistic endpoints (peripheral blood T and B cell subsets) will be analyzed using the same plan described for eGFR.

This phase I trial will provide important estimates of variability (within-subject and between-subject standard deviation) for eGFR. The estimates of variability will be valuable to power future clinical trials since these variability estimates are essential components for sample size calculations.

15. Identification and Access to Source Data

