Exploratory Endpoints	
Clinical Patient preferences and attitudes toward subcutaneous and intravenous

	
route of administration will be assessed based on questionnaires administered at enrollment and at study visits at month 6 and 12 post initiation of abatacept.
 
Immunologic/Mechanistic
 
 • CD86 receptor occupancy on PBMC will be assessed before the initial dose of abatacept, and prior to abatacept administration at months 9, and 12 months post-transplantation. • The incidence and breadth of anti-HLA antibody (including DSA) development over time (evaluated at screening, , 3, 6 and 12 post-transplant) • Peripheral blood T and B cell subsets will be assessed before initiation of abatacept and on study at 6, 9, and 12 months post - transplant.
Accrual Objective	18 patients will be enrolled into a single, investigational arm receiving abatacept
Study Duration	20 months, with the last new accrual no later than 12/31/2023.
Treatment Description	
Participants on qualifying belatacept regimen (with low dose tacrolimus, mmf and prednisone) will have their maintenance regimen changed from i.v. belatacept to s.c. abatacept, which will continue through week 52 (month 12) post-transplant:
 
Costimulation blockade:
 
 - Abatacept 125 mg subcutaneous weekly 
Background maintenance:
 
 - Tacrolimus initial trough target 3-5 ng/ml. - Mycophenylate mofetil (MMF), no less than 500 mg bid; comparable dose of mycophenolic acid (MPA) (no less than 360 mg bid) or azathioprine (AZA no less than 2mg/kg daily) may be used instead as maintenance dose. - Prednisone 5 mg po daily.
Inclusion Criteria	
 1. Must be able to understand and provide informed consent. 2. Male or Female, 18-70 years of age at the time of enrollment (all races and ethnicities). 3. Negative crossmatch (virtual or physical) at time of transplant 4. First dose of Study Drug must be given no less than 8 weeks, no more than 20 weeks post-transplant. 5. First time renal transplant who has been treated with belatacept from the time of transplant, receiving tacrolimus (target trough 3-5 ng/ml), mycophenylate mofetil (or mycophenolic acid or azathioprine), prednisone (also see exclusion criteria). 6. eGFR ≥ 40ml/min/m² (using 2021 CKD-EPI equation). 7. Must have prior documented evidence of EBV seropositivity.

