13.4 Collection and Recording of Adverse Events

13.4.1 Collection Period

Adverse events will be collected from the time of initiation of investigational treatment until a subject completes study participation, or until 30 days after he/she prematurely withdraws (without withdrawing consent) or is withdrawn from the study.

Elective hospitalization or hospital admissions for the purpose of conducting protocol mandated procedures are not to be reported as an AE unless hospitalization is prolonged due to complications and meets an SAE definition.

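### The Kaplan-Meier curves for rejection and safety run from transplantation although participants enter event-free at weeks 8–20, which distorts the early curve and labels a conditional 32–44-week incidence as a 12-month one

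*Combined protocol and SAP*

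**What the plan says.** Section 14.4 (Analysis Plan) sets the method for the primary effectiveness endpoint: "The cumulative incidence of alloimmunity (or alloimmunity-free survival) during the 12 months after transplantation will be estimated with the Kaplan-Meier method". It treats safety the same way: "The cumulative incidence of primary safety endpoints during the 12 months after transplantation will be estimated with the Kaplan-Meier method". The only rule on observation time is that participants followed for less than a year are censored at last follow-up. Delayed entry, left truncation and a first-dose origin are not mentioned. Section 14.2 defers detail to a statistical analysis plan, but nothing in the supplied text changes the origin.

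Other sections fix when a participant comes under observation:

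- Section 4.3: "First dose of Study Drug must be given no less than 8 weeks, no more than 20 weeks post-transplant".
- Section 4.4 excludes "History of any episode of biopsy-proven Banff rejection (including borderline rejection or any grade of acute TCMR) prior to enrollment" and "Evidence of CMV viremia or clinical CMV infection at any time after transplant". For BK virus it excludes only "BK viremia of greater than 4.3 DNA log copies/ml (greater than 20,000 copies/ml) at any time post-transplant".
- Section 13.4.1: "Adverse events will be collected from the time of initiation of investigational treatment until a subject completes study participation".
- Section 14.2.1 limits the modified intent-to-treat sample to those who start abatacept. Section 9.3 ends follow-up at month 12 after transplant.

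The eGFR analysis in the same Section 14.4 is on a different clock, counted from the start of abatacept.

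**The concern.** A Kaplan-Meier estimate divides each event by the number of people in whom an event could have been observed at that moment. With the clock starting at transplantation and no entry time, all 18 participants are in the denominator from day 0. None can contribute a counted rejection, CMV episode or serious adverse event before first dose. Until week 20 the risk set therefore includes people not yet under observation, and the early steps of the curve are too small.

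The second issue is the label. What is observed is incidence from conversion to month 12, in people selected for being free of rejection and CMV viremia at entry. Presented as incidence over the first 12 months after transplant, it invites comparison with rates that include the first weeks and unselected patients. The trial has one arm and is meant to inform Phase II or III design (Section 14.1), so its rates will probably be read against outside figures. Timing of rejection relative to the switch, which matters most for a conversion regimen, is also blurred.

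**Working it through.** **Inputs from the documents.** Sample size: "18 patients will be enrolled into a single, investigational arm receiving abatacept" (synopsis, Accrual Objective). First dose at weeks 8–20 (4.3). End of follow-up at week 52 after transplant (9.3 and Appendix 1). The plan states no expected rejection rate, so it has no figure of its own to reproduce here. Its one set of computed probabilities, the adverse-event table in Section 13.9, does reproduce (for example 1 − 0.90^18 = 0.85) and is not in question.

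**Which clock is meant.** On a first-dose clock the longest possible follow-up is 52 − 8 = 44 weeks, so nobody reaches one year and everyone would fall under the less-than-a-year censoring rule. That rule makes sense only on a transplant clock.

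**Built-in event-free time.** 8/52 = 15.4% and 20/52 = 38.5% of the window. Observation after first dose lasts 52 − 20 = 32 to 52 − 8 = 44 weeks. If entry is evenly spread (assumption; mean week 14) and ignoring events, the transplant clock counts 18 × 52 = 936 person-weeks, against 18 × 38 = 684 actually observed.

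**Effect on the curve (illustration).** Assume 18 participants with entry evenly spread over weeks 8–20 and two events. One is at week 14 in the participant who entered at week 8. The other is at week 30 in a participant who entered at about week 11.5.

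- As planned, everyone at risk from day 0: after week 14 the incidence is 1/18 = 5.6%. At month 12 it is 1 − (17/18)(16/17) = 2/18 = 11.1%.
- Transplant clock with delayed entry: only 9 of 18 have entered by week 14, so incidence is then 1/9 = 11.1%. At month 12 it is 1 − (8/9)(16/17) = 16.3%.
- First-dose clock: the events fall at 6 and about 18.5 weeks with all 18 observed, so the 32-week estimate is 2/18 = 11.1%.
- Events per patient-year: observed time is 684 − 38 − 22 = 624 weeks = 12.0 years, giving 2/12.0 = 0.167. The transplant clock gives 936 − 60 = 876 weeks = 16.8 years and 0.119.
- If both events fall after week 20, the planned and delayed-entry estimates are both 11.1%.

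**Effect of the label (illustration).** Assume a constant hazard, a 52-week risk p, uniform entry and no dropout. A participant entering at week e then has expected observed risk 1 − (1 − p)^((52 − e)/52).

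| Assumed 52-week risk | Entry at week 8 | Entry at week 20 | Mean over uniform entry |
|---|---|---|---|
| 10% | 8.5% | 6.3% | 7.4% |
| 20% | 17.2% | 12.8% | 15.0% |
| 30% | 26.1% | 19.7% | 22.9% |

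If the hazard is instead three times higher in weeks 0–20, simulated means for 10% and 20% are 5.5% and 11.4%. These gaps come from observing 32–44 weeks rather than 52. The simple fraction k/18, where k is the number of participants with an event, has the same gap.

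**The case against.** The strongest reply is that the month-12 number is not biased for the endpoint as defined. With complete follow-up, the planned Kaplan-Meier value at month 12 is k/18, which is the complement of the proportion free of rejection in Section 3.2. Changing the origin does not change the event count. This stands.

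A reader might go further and infer that the estimator itself pulls the month-12 rejection figure down and makes abatacept look better than it is. The documents do not support that. The fall from 10% to 7.4% is a consequence of the entry window. A 52-week risk on drug is not something this trial can observe. The plan also names no comparator, success threshold or test for rejection, and the study stopping rules in Section 12.6 use event counts, which are unaffected. Nor would a first-dose origin make the headline less favorable: under constant hazard the 32-week figure is 6.3% or 12.8%, below the planned 7.4% or 15.0%.

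Three further points limit the concern:

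- The origin is inferred from the wording of the window. The censoring rule makes the inference strong but not certain.
- It would be too broad to say that no safety event can predate entry. BK viremia up to 20,000 copies/ml is allowed before enrollment, so the argument is inexact for the lower BK strata. For serious adverse events, the early weeks are event-free only because collection has not started.
- Delayed entry is fragile at this size. Events at weeks 10 and 14 would give 1 − (2/3)(7/8) = 41.7% from two events in 18.

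None of this repairs the risk sets before week 20, or makes the stated label describe what is observed.

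**Conclusion.** The point holds in a limited form. Read as written, Section 14.4 uses the wrong time origin for participants who come under observation at weeks 8–20. Any event before week 20 is divided by too many people, and the result carries a first-year label that it has not earned. The distortion of the curve depends on when events fall: none if all come after week 20, and 11.1% against 16.3% in the worked example. The month-12 fraction is arithmetically sound, and its fault is one of labeling and comparability. How far it would fall short of a full first-year rate depends on assumed hazards and entry times, so the percentages above are illustrations and not estimates for this trial. No planned test or stopping decision changes. The correction should still be made before analysis, because it affects the primary effectiveness curve and most of the primary safety curves.

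**What to change.** In Section 14.4 and the statistical analysis plan:

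- Set time zero at first abatacept dose for the Kaplan-Meier analyses, and censor at week 52 after transplant or at last follow-up.
- Report the estimate at 32 weeks after first dose, the horizon every participant can reach. Show the curve to 44 weeks with numbers at risk, and add events per patient-year.
- Keep the month-12 fraction, labeled as running from conversion to month 12 post-transplant among patients rejection-free at conversion. State that it is not comparable with full first-year rates.
- If a transplant-clock curve is also shown, use delayed entry and warn that it is unstable while few are at risk. Such a curve still says nothing about the weeks before the first entry.
- For the lower BK strata, say how viremia already present at first dose is handled.

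The cost is wording only, with no new data. The reported horizon is shorter, and the 32-week figure will usually be numerically lower than the month-12 fraction. It must therefore always carry its horizon and never be presented as a 12-month rate.
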